8.4.1 Inclusion Criteria

The following criteria must be met by all subjects/patients considered for study participation:

1. Willing and able to give written informed consent for participation in the study and is willing and able to abide by the study restrictions.
2. Males and females aged between 18 and 65 years (inclusive) at Screening. For patients in the RA cohort, an age interval between 18 and 70 years (inclusive).
3. Normal clinically physical findings, apart from RA specific findings (including deviating laboratory values e.g., mild anaemia or swollen joints) for RA patients, including pulse rate, blood pressure, electrocardiogram (ECG), physical examination, and laboratory values (haematological/clinical chemistry) as judged by the Investigator. Healthy subjects must be negative for anti-CCP and have Rheumatoid Factor <1.5 ULN at Screening.
4. For Parts 1 and 3, body mass index (BMI) between 19.0 and 30.0 kg/m² and body weight between 50 to 100 kg (inclusive) at Screening. For Part 2, body weight between 50 to 120 kg (inclusive) at Screening.
5. *Sexually active male patients* participating in the study must use a barrier method of contraception (condom) and refrain from sperm donation during the study and for at least 150 days after last dosing if their female sexual partner is of childbearing potential. Acceptable methods of birth control for female partners of male subjects are: hormonal contraceptives (oral contraceptives, implant or injection), intrauterine device (placed at least 1 month before the start of the study). Surgical sterilization of male patients can be

² The optional 6th cohort in healthy subjects was not run

accepted as a form of birth control if the sterilization procedure took place at least 6 months prior to the start of the study.

6. *Females of childbearing potential* must during the study and for at least 230 days after last dosing utilise a method of contraception that can achieve a failure rate of less than 1% per year when used consistently and correctly. Such highly effective birth control methods include:
 - combined (estrogen and progestogen containing) hormonal contraception associated with inhibition of ovulation:
 - oral
 - intravaginal
 - transdermal
 - progestogen-only hormonal contraception associated with inhibition of ovulation:
 - oral
 - injectable
 - implantable
 - intrauterine device (IUD)
 - intrauterine hormone-releasing system (IUS)
 - bilateral tubal occlusion
 - vasectomized partner

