7.7.3.4 Safety Clinical Laboratory Evaluations

Laboratory parameters to be determined per protocol are:

Hematology	Chemistry	Urinalysis	Others
Hemoglobin	Creatinine and eGFR	Nitrates	FSH ^b
Hematocrit (packed cell volume [PCV])	Fasting glucose ^d	pH	Beta-HCG ^b
RBC count	Sodium	Glucose	
Platelet count	Potassium	Albumin or micro albumin	
WBC count	ALT	Erythrocytes	
Neutrophils	AST	Leukocytes	
Eosinophils	GGT	Ketones	
Monocytes	Bilirubin (total, direct and indirect)	Microscopy ^a	
Basophils	Alkaline phosphatase	Specific gravity	
Lymphocytes	Albumin	Creatinine	
Mean corpuscular volume	Cholesterol (total) – lipid status ^d	Protein	
Mean corpuscular hemoglobin ^f	LDL – lipid status ^d		
Mean corpuscular hemoglobin concentration ^f	HDL – lipid status ^d		
Erytoblasts ^f	Triglycerides – lipid status ^d		
Red blood cell distribution width (RDW-CV) ^f	LDH – lipid status ^d		
ESR	α-tocopherol ^e Rheumatoid factor ^c Chloride CRP hsCRP (Part 2 only) Calcium (corrected) Inorganic phosphate Uric acid Blood urea nitrogen Pancreatic lipase ^g		

^a If there is an abnormality in urine in accordance with the clinical laboratory standard procedures.

^b Required of postmenopausal females only during Screening.

^c Only at Screening.

^d Only at Screening, pre-dose on Day 1, Day 14 and Day 35 (Parts 1 and 2). For Part 3 at Screening and Day 169 (EOS).

^e Only pre-dose on Day 1, Day 14 and Day 35 (Parts 1 and 2). For Part 3 at Screening and Day 169 (EOS).

^f Only applicable for Part 2

^g Not on Day 92 of Part 3

Listings will be created of the laboratory data according to protocol and only present the original values, units and reference ranges as received from the laboratory.

All qualitative laboratory data will be supplied per lab manual, which is checked on the use of International System (SI) units by clinic and (if necessary) converted to SI units for the descriptive statistics.

Listings of all clinical laboratory data for each subject will be provided and values outside the normal range are flagged. For continuous data, abnormal values will be flagged with 'L' (low) for values below the lower limit of the laboratory's normal range, or 'H' (high) for values above the upper limit of the laboratory's normal range. Qualitative results outside of the laboratory's normal range will be flagged as 'A' (Abnormal). For evaluations (Normal, Abnormal NCS and Abnormal CS), the count and percentage will be provided.

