Laboratory safety data will be summarized according to protocol scheme time point. Where applicable, change from baseline will also be calculated and summarized. Baseline is defined as the last value measured on Day -1 (or pre-dose on Day 1) The evaluations from baseline over time will be summarized as a shift table.

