14.3.1.2	Treatment-Emergent Adverse Events - MedDRA	Adverse event summary containing the number and percentage of subjects experiencing TEAEs. TEAEs are tabulated by SOC and PT and summarized by treatment groups. The summary will be presented in descending according to SOC and PT.
14.3.1.3	Treatment-Emergent Adverse Events by Intensity - MedDRA	The same tabulation as 14.3.1.2 will be created for TEAEs by intensity.
14.3.1.4	Treatment-Emergent Adverse Events by Relationship - MedDRA	The same tabulation as 14.3.1.2 will be created for TEAEs by relationship to study drug.
14.3.1.5	Treatment-Emergent Adverse Events - MedDRA (Preferred Term over XX %)	Adverse event summary containing the number and percentage of subjects experiencing TEAEs. TEAEs are tabulated by PT and summarized by treatment groups.
14.3.1.6	Treatment-Emergent Serious Adverse Events - MedDRA	The same tabulation as 14.3.1.2 will be created for TESAEs.
14.3.1.7	Treatment-Emergent Serious Adverse Events by Intensity - MedDRA	The same tabulation as 14.3.1.2 will be created for TESAEs by intensity.

14.3.1.8	Treatment-Emergent Serious Adverse Events by Relationship - MedDRA	The same tabulation as 14.3.1.2 will be created for TESAEs by relationship to study drug.
14.3.2.1	Listing of Subjects with Treatment-Emergent Serious Adverse Events	Listing for all TESAE.
14.3.2.2	Listing of Subjects with Treatment-Emergent AEs Leading to Death	Listing for AEs leading to death.
14.3.2.3	Listing of Subjects with Treatment-Emergent AEs Leading to Premature Discontinuation of Study Drug	Listing for AEs leading to premature discontinuation.
14.3.4	Abnormal Laboratory Values for All Subjects	A subject listing of all data outside the (investigators) reference range, containing the variables test, age, sex, date/time, unit, value, reference range, and whether there were clinical implications (NCS/CS).
14.3.5.1- 14.3.5.3	Laboratory Values over Time - Hematology/ Serum Biochemistry/ Urinalysis	Descriptive statistics for values and change from baseline by time point, per treatment groups.
14.3.5.4- 14.3.5.6	Individual Subject Changes (Shift Table) - Hematology/ Serum Biochemistry/ Urinalysis	Shift table for LB data.
14.3.6	Summary of Vital Sign	Descriptive statistics for values and change from baseline by time point, per treatment groups.
14.3.7- 14.3.8	Summary of 12-Lead ECG/ 3-Lead ECG (Telemetry)	Descriptive statistics for values and change from baseline by time point, per treatment groups.

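### As worded, the SAP's laboratory shift tables grade results only as Normal, Abnormal NCS or Abnormal CS, so for continuous tests they do not show whether a value moved high or low

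*SAP*

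**What the plan says.** SAP 7.7.3.4 sets out two ways of classifying a laboratory result.

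- **Direction, for listings.** The SAP says: "Listings of all clinical laboratory data for each subject will be provided and values outside the normal range are flagged". For continuous tests, "abnormal values will be flagged with 'L' (low) for values below the lower limit of the laboratory's normal range, or 'H' (high", the latter for values above the upper limit. Qualitative results receive a single abnormal flag.
- **Significance grade, for tables.** "For evaluations (Normal, Abnormal NCS and Abnormal CS), the count and percentage will be provided".

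The next paragraph, on summaries by time point, ends: "The evaluations from baseline over time will be summarized as a shift table". In the table list of SAP 10.2, the matching entry for 14.3.5.4 to 14.3.5.6 is "Individual Subject Changes (Shift Table) - Hematology/ Serum Biochemistry/ Urinalysis". Its note says only that this is a shift table of laboratory data. For full layouts the SAP refers to a separate mock table document, which was not among the documents available.

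Tables 14.3.5.1 to 14.3.5.3 give descriptive statistics for values and change from baseline. Table 14.3.4 lists each out-of-range value with its reference range and significance grade.

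**The concern.** Laboratory results belong to the primary endpoint (protocol 8.1.1), and the analysis is purely descriptive (SAP 7.1), so the safety tables are the evidence. The usual purpose of a shift table is to count how many subjects left the normal range and on which side. Many laboratory signals have a side: the laboratory items in protocol 8.7.2 concern low leukocytes, neutrophils and platelets, and raised liver tests and creatinine. They are cited here only to show that direction carries meaning.

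If the shift table uses only the significance grade, a subject whose neutrophils fall below range and one whose neutrophils rise above it are counted together. The tables are titled as individual subject changes but would not say which way anyone changed. No other listed table counts subjects by baseline and post-baseline direction.

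**Working it through.** The plan states no figure on this point, so the check is a reading of the text followed by an enumeration.

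**Step 1: which categories the shift table uses.** The shift sentence refers to *the evaluations*. The preceding paragraph of the same section gives that term three levels: Normal, Abnormal NCS, Abnormal CS. SAP 7.7.3.5 to 7.7.3.7 use the term with the same three levels for vital signs, 12-lead ECG and telemetry. The L and H flags appear only in the text about listings. Nothing in the SAP or protocol gives the shift tables Low/Normal/High categories.

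**Step 2: underlying states.** Assume that for a continuous test an abnormal grade goes with a value below or above range. A result then has five possible states: Normal (N), High NCS, High CS, Low NCS, Low CS. Baseline by post-baseline gives 5 × 5 = 25 transitions.

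**Step 3: map them to the 3 by 3 table.** Each cell holds these directions (H high, L low):

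| Baseline | To Normal | To Abnormal NCS | To Abnormal CS |
|---|---|---|---|
| Normal | N→N | N→H, N→L | N→H, N→L |
| Abnormal NCS | H→N, L→N | H→H, H→L, L→H, L→L | H→H, H→L, L→H, L→L |
| Abnormal CS | H→N, L→N | H→H, H→L, L→H, L→L | H→H, H→L, L→H, L→L |

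Check on the count: 1 + 4 × 2 + 4 × 4 = 25.

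**Step 4: read off the results.**
- All 6 off-diagonal cells contain more than one direction, so no displayed shift identifies a rise or a fall.
- High-to-low transitions: 2 baseline grades × 2 post-baseline grades = 4. Two of them (NCS to NCS, CS to CS) lie on the diagonal and appear as no shift. The other two appear as a change of grade without direction. Low-to-high behaves in the same way.

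**Step 5: the alternative.** On a Low/Normal/High by Low/Normal/High table, each of the 6 off-diagonal cells holds one direction, and every high-to-low or low-to-high change is off the diagonal. That table has its own blind spot. High NCS to High CS, High CS to High NCS, and the two matching low transitions (4 in all) would fall on its diagonal. The two displays answer different questions, and neither replaces the other.

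These counts are types of transition, not expected numbers of subjects.

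**The case against.** The case on the other side has several parts.

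- **The categories are inferred.** The section title itself uses the word evaluations in a general sense, the table note is bare, and the SAP leaves the details to shells not seen here. This stands as a limit on certainty. The three-level reading is still the natural one, and if the shells already use Low/Normal/High, the SAP should say so.
- **Direction is reported elsewhere.** This stands. The listings carry L and H flags, and Table 14.3.4 shows each abnormal value against its range. SAP 7.1 requires the median, minimum and maximum as well as the mean, so the largest fall and largest rise in a group are visible. Clinically significant abnormalities are also reported as adverse events. With 6 active subjects per cohort, the listings can be read in full. What none of this supplies is a count of subjects leaving the range on each side.
- **The shift table is an extra.** Protocol 10.4 does not call for one, and a significance shift answers a legitimate question. This stands, and is why the existing shift should be kept.

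A reader might also infer stronger points that the documents do not support.

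- *Part 2 will produce many high-to-low moves.* RA patients may enter with normal findings "apart from RA specific findings (including deviating laboratory values e.g., mild anaemia or swollen joints) for RA patients". The laboratory example there is anaemia, a low value, and low to low is no shift on either scale.
- *The table would miss the 8.7.2 criteria.* Those are numerical thresholds that the safety review committee assesses during the study. Neither form of shift table tests them.

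**Conclusion.** The point holds as a weakness of presentation. On the SAP's wording, Tables 14.3.5.4 to 14.3.5.6 give no high or low direction for continuous tests in a primary-endpoint domain. The practical core is the move from Normal to Abnormal, where new low and new high values are counted together. Full reversals across the normal range would be hidden only when the grade is unchanged (2 of 4 transitions), and the documents give no reason to expect many.

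It would be wrong to conclude that every high-to-low change disappears, or that directional data are lost from the report.

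The verdict rests on reading *evaluations* as the three-level grade and on mock shells that could not be checked. It does not apply to qualitative results such as dipstick urinalysis, which have no high or low side.

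**What to change.** In SAP 7.7.3.4 and in the notes to Tables 14.3.5.4 to 14.3.5.6, state the shift categories. For continuous parameters, add a table of baseline Low/Normal/High by post-baseline Low/Normal/High, by treatment group, using the L and H flags already derived for the listings. Keep the shift in Normal, Abnormal NCS and Abnormal CS beside it, because substitution would hide a high value that worsens from not significant to significant. A single crossed scale (Low CS, Low NCS, Normal, High NCS, High CS) would also serve, although 25 cells for 6 active subjects would be sparse. Qualitative urinalysis stays Normal/Abnormal. Align the mock shells with the text.

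The cost is a sentence or two in the SAP and one extra set of tables from existing data. No new data are collected and no assessment changes.

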7.7.3.5 Vital Signs

Vital signs (systolic BP, diastolic BP, pulse rate, SpO₂, and temperature) collected according to protocol will be summarized using descriptive statistics for each time point. Where applicable, change from baseline will be calculated. For evaluations (Normal, Abnormal NCS and Abnormal CS), the count and percentage will be provided.

7.7.3.6 12-lead ECG

Twelve-lead electrocardiogram parameters (heart rate, PR, QRS - duration, QT, QTcB, QTcF, QTcB average, and QTcF average) collected according to protocol will be summarized using descriptive statistics for each time point. Where applicable, change from baseline will be calculated. The count and percentage of evaluations (Normal, Abnormal NCS and Abnormal CS) will be summarized according to protocol scheme time as well.

7.7.3.7 3-lead ECG (Telemetry)

Three-lead electrocardiogram collected evaluation according to protocol will be summarized using descriptive statistics on Day 1. For evaluations (Normal, Abnormal NCS and Abnormal CS), the count and percentage will be provided.

7.7.3.8 RA Previous and Concomitant Medication

RA previous medication and concomitant medications will be coded according to the latest version (version 2022 or higher) of the WHO drug code and the ATC class code. And will be summarized in descending order according to the ATC level 2, ATC level 4, and generic name using the number and percentage of subjects taking, as well as the number of events.

8 CHANGES FROM PROTOCOL AND OTHER REMARKS

There were no significant changes to the analyses planned in the study protocol.

9 SOFTWARE

9.1 Coding Systems

Adverse Events, Medical History, and Concomitant Medication will be coded as described in the Data Management documentation.

9.2 Statistical Software

The statistical analysis and reporting will be done using SAS for Windows™ version 9.4 or higher. SAS output will be saved and imported into PDF.

9.3 Reporting

All output will be generated as SAS tables and listings. All tables and listings will be created such that they fit landscape pages. All tables and listings will be created using SAS with an PDF output, and font Courier New size 9 will be used.

A list of tables and listings is presented (per report section) in [Section 10](#).

The QPS template tables and listings will be used, and a separate templates document will be supplied together with the SAP. Adaptations to template layout are possible depending on the design of the study, the length of variables and the number of variables. It should be noted that all data as collected will be presented in listings and/or tabulations. The examples in the templates document may not cover all possible collected data, or examples may be present of data not collected for this specific study.

All tables and listings created will need to adhere to the following margins to fit the appendix layout if the CSR:

Landscape: Top - 1.14 inch
 Bottom - 0.79 inch
 Left - 1 inch
 Right - 1 inch

10 TABLES, LISTINGS AND FIGURES

10.1 List of Tables and Figures – core text

All tables mentioned here will be presented in the report and will be supplied to the Medical Writer as separate .RTF or .DOCX files.

- Summary table of demographic data, baseline parameters, and concomitant medications for all-treated set: mean, median, standard deviation, minimum, maximum, and number of

available observations for continuous variable. Counts and percentages for qualitative characteristics.

- Adverse event summary containing the number and percentage of subjects experiencing any TEAE or TESAE. Table will contain information concerning the intensity and relationship and discontinuation due to an AE. Table will be presented by treatment groups.
- Adverse event summary containing the number and percentage of subjects experiencing TEAEs. AEs are tabulated by SOC and PT and summarized by treatment groups. AEs will be summarized in descending order according to incidence of SOC and PT.
- If applicable, the same tabulations will be presented for TESAEs.
- If applicable, summary listing of TESAEs containing description of event, MedDRA preferred term, subject number, intensity, action taken, relationship, and outcome.

10.2 List of Tables – end of text

All tables mentioned here will be presented according to ICH guidelines in appendix 14 of the report. A complete document (batch load) will be created in Word for the Medical Writer, in the order and with section number and title as stated.

Mock table is provided as a separate document to this SAP.

- 14.1 Demographic Data Summary figures and tables
- 14.2 Efficacy Data Summary figures and Tables
- 14.3 Safety Data Summary figures and tables
 - 14.3.1 Displays of Adverse Events
 - 14.3.2 Listings of Deaths, Other Serious and Significant Adverse Events
 - 14.3.3 Narratives of Deaths, Other Serious and Certain Other Significant Adverse Events
 - 14.3.4 Abnormal Laboratory Value Listing (each subject)

Section	Title	Notes
14.1.1	Summary of Subject Disposition	Summary of all eligible, randomized, receiving study drug, completed subjects, the number of subjects in the all-treated set, immunogenicity set, per-protocol set, and safety set by treatment groups.
14.1.2	Summary of Demographics, Baseline Parameters, and Concomitant Medications	Descriptive statistics for demographic data, baseline parameters and CM for all-treated set by treatment groups.
14.2.1	Summary of Bile Salt-Stimulated Lipase (BSSL) in Blood	Descriptive statistics for absolute values and change from baseline by time point, per treatment groups.

14.2.2	Summary of Serum C-reactive Protein (CRP)	Descriptive statistics for absolute values and change from baseline by time point, per treatment groups.
14.2.3	Summary of Erythrocyte Sedimentation Rate (ESR)	Descriptive statistics for absolute values and change from baseline by time point, per treatment groups.
14.2.4	Summary of Immunogenicity	Descriptive statistics for absolute values and change from baseline by time point, per treatment groups.
14.2.5	Summary of S-Calprotectin	Descriptive statistics for absolute values and change from baseline by time point, per treatment groups.
14.2.6	Summary of hsCRP	Descriptive statistics for absolute values and change from baseline by time point, per treatment groups.
14.3.1.1	Treatment-Emergent Adverse Events	Adverse event summary containing the number and percentage of subjects experiencing any TEAE or TESAE. Table will contain information on the intensity, action taken, relationship to study drug, outcome, and serious of AE. Table will be presented by treatment groups.
14.3.1.2	Treatment-Emergent Adverse Events - MedDRA	Adverse event summary containing the number and percentage of subjects experiencing TEAEs. TEAEs are tabulated by SOC and PT and summarized by treatment groups. The summary will be presented in descending according to SOC and PT.
14.3.1.3	Treatment-Emergent Adverse Events by Intensity - MedDRA	The same tabulation as 14.3.1.2 will be created for TEAEs by intensity.
14.3.1.4	Treatment-Emergent Adverse Events by Relationship - MedDRA	The same tabulation as 14.3.1.2 will be created for TEAEs by relationship to study drug.
14.3.1.5	Treatment-Emergent Adverse Events - MedDRA (Preferred Term over XX %)	Adverse event summary containing the number and percentage of subjects experiencing TEAEs. TEAEs are tabulated by PT and summarized by treatment groups.
14.3.1.6	Treatment-Emergent Serious Adverse Events - MedDRA	The same tabulation as 14.3.1.2 will be created for TESAEs.
14.3.1.7	Treatment-Emergent Serious Adverse Events by Intensity - MedDRA	The same tabulation as 14.3.1.2 will be created for TESAEs by intensity.

14.3.1.8	Treatment-Emergent Serious Adverse Events by Relationship - MedDRA	The same tabulation as 14.3.1.2 will be created for TESAEs by relationship to study drug.
14.3.2.1	Listing of Subjects with Treatment-Emergent Serious Adverse Events	Listing for all TESAE.
14.3.2.2	Listing of Subjects with Treatment-Emergent AEs Leading to Death	Listing for AEs leading to death.
14.3.2.3	Listing of Subjects with Treatment-Emergent AEs Leading to Premature Discontinuation of Study Drug	Listing for AEs leading to premature discontinuation.
14.3.4	Abnormal Laboratory Values for All Subjects	A subject listing of all data outside the (investigators) reference range, containing the variables test, age, sex, date/time, unit, value, reference range, and whether there were clinical implications (NCS/CS).
14.3.5.1- 14.3.5.3	Laboratory Values over Time - Hematology/ Serum Biochemistry/ Urinalysis	Descriptive statistics for values and change from baseline by time point, per treatment groups.
14.3.5.4- 14.3.5.6	Individual Subject Changes (Shift Table) - Hematology/ Serum Biochemistry/ Urinalysis	Shift table for LB data.
14.3.6	Summary of Vital Sign	Descriptive statistics for values and change from baseline by time point, per treatment groups.
14.3.7- 14.3.8	Summary of 12-Lead ECG/ 3-Lead ECG (Telemetry)	Descriptive statistics for values and change from baseline by time point, per treatment groups.
14.3.9	Summary of Injection Site Reaction	Descriptive statistics by time point, per treatment groups.
14.3.10	Summary of RA Previous and Concomitant Medication by ATC Level	Summary containing the number and percentage of subjects taking RA previous and concomitant medication by ATC Level.

Full details are provided in SAP Mock Table.

